2.3.2 Secondary objectives

- 1. To assess participants response (treatment efficacy) to varying dose concentrations, dose frequency, length of treatment, and formulation of *Artemisia afra* treatment.
- 2. To identify the most acceptable dose concentration, dose frequency, length of treatment, and formulation (flavor) of Artemisia treatment.
- 3. To assess the safety (ASE) of *Artemisia afra* treatment in participants by dose concentration, dose frequency, length of treatment, and formulation. As a commonly used tea, no toxicity is expected.
- 4. To assess variability of plasmodium test predictive values between mRDT, rtPCR, and direct blood smear observation in asymptomatic persons.

Treatment outcomes

Major outcome

• Decrease in parasite load over time.

Secondary outcomes

- Decrease in gametocyte load in carriers with Artemisia afra tea by dose concentration, dose frequency, length of treatment, and formulation.
- Acceptability (adherence and completion) of *Artemisia afra* treatment by dose concentration, dose frequency, length of treatment, and formulation (flavor).

- Safety (SAEs) of *Artemisia afra* treatment in participants by dose concentration, dose frequency length of treatment, and treatment formulation.
- Absolute increase in Cycle threshold (Ct >20).
- Likelihood and variability in the rate of reservoir elimination with treatment, compliance/ acceptability, and occurrence of side effects /adverse events in different treatment arms.

Treatment endpoints

Primary endpoints

• Proportion of people with decreased gametocyte load after treatment with *Artemisia afra* tea on Day 35 from baseline.

Secondary endpoints

- Level of decrease in gametocyte load (rt-PCR Ct) in the different treatment arms at D7, D14, D28, and D35 from baseline (activity level and optimal dosage schedule).
- Level of decrease in gametocyte load the various treatment arms (rt-PCR Ct) by gender, age, and trial entry parasite load, at D7, D14, D28, and D35 from baseline.
- Absolute increase in Cycle threshold (Ct >20) in various treatment arms at D7, D14, D28, and D35 from baseline.
- Proportion of people in the various treatment arms who respect and complete the prescribed treatment dosages (accepted dosage schedule and drug formulation).
- Proportion of persons on the various arms of treatment who develop clinical symptoms at D7, D14,
 D28, and D35 from baseline.

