- Proportion of people on the various arms of treatment who develop ASEs or AEs at D7, D14, D28, and D35 from baseline (No severe adverse side effects are expected).
- Proportion of persons on the various arms of treatment who withdraw from study due to severe ASEs or AEs at D7, D14, D28, and D35 from baseline.
- Proportion of persons on the various arms of treatment who withdraw from study for reasons other than severe AEs at D7, D14, D28, and D35 from baseline.
- Proportion of persons with baseline discordant test results (False positive or false negative) between mRDT, rt PCR, and direct blood smear observation?

Exploratory endpoints

- Variability in level of decease in gametocyte load (rt-PCR Ct) in the various treatment arms at D7, D14, D28, and D35 from baseline.
- Variability in level of decease in gametocyte load (rt-PCR Ct) in the various treatment arms by gender, age, and trial entry parasite load, at D7, D14, D28, and D35 from baseline.
- Variability in attainment of absolute increase in Cycle threshold (Ct >20) in the various treatment arms at D7, D14, D28, and D35 from baseline.

- Variability in the proportion of participant who respect and complete prescribed treatment dosages (acceptability) in the various treatment arms.
- Variability in the proportion of participants who develop clinical symptoms in the various treatment arms at D7, D14, D28, and D35 from baseline.
- Variability in the proportion of participants who develop Severe ASEs in the various treatment arms at D7, D14, D28, and D35 from baseline (not expected).
- Variability in proportion of participants who withdraw from the study due to severe ASEs, in the various treatment arms, at D7, D14, D28, and D35 from baseline.
- Variability in proportion of participants who withdraw from the study for reasons other than severe AEs, in the various arms of treatment at D7, D14, D28, and D35 from baseline.

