Randomization: Prior to treatment, eligible participants will be randomly assigned into the 8 study arms. The randomization method will be a permuted block randomization, with a block size of either 14 or 28 at random, and with a two-to-one allocation ratio for each active arm against two different control arms (2:2:2:2:2:1:1).

Blinding: The participants in the intervention arms will be aware of their assignment to an intervention group but unaware of the treatment assigned to them. The site staff (investigators or observers) will be

aware of assignments to one control arm (regular tea group), but unaware of assignments in the other treatment arms.

Visits/assessment schedules: A total of five study visits will be effected, being one baseline visit on Day 0, and four follow-up visits on Day 7, 14, 28 and 35, from baseline. During the baseline visit plasmodium tests targeting specific parts of the gametocyte genes will be done to determine the participants' initial (baseline) parasite load, and during subsequent visits, follow up control tests (rtPCR and blood smear) will be done, and the gametocyte load recorded, alongside assessments for clinical symptoms and adverse sides effects (if any).

Endpoints The efficacy of each of the treatment dosage schedule will be evaluated on day 7,14,28 and 35 from baseline, based on response to treatment or reservoir elimination rate. Response to treatment will be indicated by an absolute increase in Cycle threshold (Ct >20), or a negative rt-PCR tests results (Ct >40). If the patient misses the follow-up visit, compliance will be noted in the completion worksheet (filled out at end of study) and the parasite load and adverse side effects noted during the last visit considered. No severe side adverse effects are expected from the treatment but since toxicity is always a concern in clinical trials involving humans, participants will be observed for any severe ASEs and withdrawal noted throughout the study duration.

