5.6 Study visits

Table 4: Study visits

Visit time	Activity					
1st: Day 0	- Baseline assessments and recording					
	- Screening for presence pf plasmodium parasites (mRDT, qPCR)					
	- Parasite load assessment (rtPCR)					
	- Recruitment, randomization, and allocation.					
	 Treatment prescription and education on treatment administration. 					
2 nd : Day 7	- Parasite load measurement (rtPCR)					
	- Monitoring and recording of:					
	o ASEs and AEs.					
	 Treatment compliance /acceptability (dosage respect) 					
	 Number of withdrawals and reasons, 					
	 Occurrence of clinical symptoms 					
	 Concomitant medications 					
3 rd : Day 14	- Parasite load measurement (rtPCR)					
	- Monitoring and recording of:					
	 ASEs and AEs. 					
	 Treatment compliance /acceptability (dosage respect) 					
	 Number of withdrawals and reasons, 					
	 Occurrence of clinical symptoms 					
	o Concomitant medications					

4th: Day 28	- Parasite load measurement (rtPCR)			
	 Monitoring and recording of: 			
	- Wolltoring and recording or.			
	o ASEs and AEs.			
	 Treatment compliance /acceptability (dosage respect) 			
	 Number of withdrawals and reasons, 			
	Occurrence of clinical symptoms			
	 Concomitant medications 			
5 th : Day 35	- Parasite load measurement (rtPCR)			
	- Monitoring and recording of:			
	o ASEs and AEs.			
	 Treatment compliance /acceptability (dosage respect) 			
	 Number of withdrawals and reasons, 			
	 Occurrence of clinical symptoms 			
	 Concomitant medications 			

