5.7 Laboratory tests

Before randomization during the baseline visit (D0), blood samples will be collected from each participant and examined for the presence of parasites (Gametocytes) using Malaria rapid diagnostic test kit (BIOCREDIT Malaria Ag P.f/Pan RDT). RDT positive samples will be re-examined with qPCR (quantitative polymerase chain reaction) and direct microscopy for confirmation. The qCPR will be repeated for negative samples and participants excluded if still negative. All qPCR positive samples will be further analyzed with rt PCR (real time polymerase chain reaction), for parasite quantification and specific stage identification, targeting specific parts of the gametocyte genes.

- a. *BIOCREDIT Malaria Ag P.f/Pan RDT*: This is a three-band RDT that detects HRP2 and pan-pLDH antigens which will detect the presence of P. falciparum (HRP2) and of another specie (pan-pLDH). Results will be interpreted as Negative (band absent) Mildly positive (faint band appearance) strongly positive (conspicuous band appearance).
- b. *Direct microscopy*: Direct Microscopic identification of parasites will be performed using thin and thick blood films stained with Giemsa and quantified as number of parasites per milliliter of blood.
- c. *rtPCR*): The parasite load will be measured based on the number of rtPCR cycle thresholds (Ct) (which is an inverse proportion of the parasite load) and classified as absolute increase in Cycle threshold (Ct >20), or negative rt-PCR tests results (Ct >40).
- d. *Blood sample schedule*: Five blood samples (approximately 1mL each) will be collected at Visit 1 (Day 0), Visit 2 (Day 7), Visit 3 (Day 14), Visit 4 (day 28), and visit 5 (day 35). After conducting the 3 or 4 tests at visit 1, only the rtPCR test and blood smear microscopy will be done during subsequent evaluations.

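### The decrease in load is reported by entry load, but both come from the same single Day 0 measurement, so regression to the mean tends to give a false gradient by load within every arm

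*Protocol*

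**What the plan says.** The secondary endpoints in Section 2.3.2 (also in the Synopsis) include "Level of decrease in gametocyte load the various treatment arms (rt-PCR Ct) by gender, age, and trial entry parasite load", at Days 7, 14, 28 and 35 from baseline. The exploratory endpoints add "Variability in level of decease in gametocyte load (rt-PCR Ct) in the various treatment arms by gender, age, and trial entry parasite load".

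On how entry load is obtained:
- Section 3, Visits/assessment schedules, says of the baseline visit that "plasmodium tests targeting specific parts of the gametocyte genes will be done to determine the participants' initial (baseline) parasite load".
- Section 5.7 gives the scale: "The parasite load will be measured based on the number of rtPCR cycle thresholds (Ct) (which is an inverse proportion of the parasite load". A higher Ct therefore means a lower load.
- Section 5.6, Table 4, lists one rtPCR load assessment on Day 0.
- Section 5.7 plans one blood sample per visit, and Day 0 is the only visit before treatment. The only repeat concerns the confirmatory test: "The qCPR will be repeated for negative samples and participants excluded if still negative".

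Section 8.3 plans descriptive statistics by arm and time, and a linear mixed model to compare groups. It does not say how baseline enters that model.

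**The concern.** Read together, these sections make the grouping value and the subtracted value the same single Day 0 Ct. If Day 0 happened to be a high-load day for a participant, that chance excess places the participant in the high-load group and also enlarges the later decrease. A chance low does the opposite. A table of decreases by entry load thus has a gradient built in, in the active and placebo arms alike.

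The primary objective is to find the activity level and the optimal dosage. A larger decrease among heavy carriers would naturally be read as a finding about where the tea works, when part or all of it could be this artefact.

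**Working it through.** **No figure to reproduce.** The protocol gives no Ct SD, no within-person correlation and no cut-point for entry load. The values below are assumptions, shown as ranges.

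**Formula.** Let Y0 and Y1 be the Day 0 and follow-up Ct, with common mean μ, common SD, correlation ρ and no drug effect. Then

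E[Y1 − Y0 | Y0] = −(1 − ρ)(Y0 − μ).

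For a normal variable, each half of a median split lies on average √(2/π) = 0.798 SD from the mean. With stable load and no selection, Ct changes by +0.798(1 − ρ)SD in the high-load half (an apparent fall in load) and by the same amount downwards in the low-load half.

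**Numbers for between-person SD 3.**
- Visit-to-visit SD 1: total SD = √(9 + 1) = 3.16 and ρ = 9/10 = 0.90. Shift = 0.798 × 0.10 × 3.16 = 0.25 cycles, so the gap between halves is 0.5.
- Visit-to-visit SD 2.5: total SD = √(9 + 6.25) = 3.91 and ρ = 9/15.25 = 0.59. Shift = 0.798 × 0.41 × 3.91 = 1.28 cycles, so the gap is about 2.5.

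If one cycle is taken as a twofold change, this is 2^0.5 = 1.4-fold to 2^2.5 = 5.7-fold in load. The share with any decrease is 57% against 43% at the lower end and about 65% against 36% at the upper end. Over a wider range (total SD 2 to 5, ρ 0.3 to 0.95) the shift per half runs from 0.08 to 2.79 cycles.

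**Effect of enrolment selection.** Section 4, Table 3, requires positive RDT and qPCR at entry. This was simulated as selection on a Day 0 marker correlated with Ct (SD 4, ρ 0.7, 10% selected, no drug effect). Positive values are apparent falls in load, in cycles.

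| Correlation of marker with Ct | High-load half | Low-load half | Gap |
|---|---|---|---|
| no selection | +0.96 | −0.96 | 1.92 |
| 0.3 | +1.55 | −0.27 | 1.82 |
| 0.6 | +2.05 | +0.47 | 1.58 |
| 1.0 | +2.47 | +1.73 | 0.74 |

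In every scenario run the high-load half fell, and fell more than the low-load half. The sign in the low-load half depends on how strong the selection is.

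**How often it would look significant with no effect.** For ρ = 0.9, 0.7 and 0.5, a high-versus-low difference reaches P < 0.05 in 10%, 22% and 33% of simulated trials within one active arm (8 × 2 sites = 16). If all 96 active participants (6 × 16) are pooled, the figures are 43%, 88% and 99%.

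**Contrast with control.** There are 2 × 4 × 2 = 16 controls. In null simulations, the active-minus-control difference in change within the high-load half averaged −0.004 to −0.008 cycles, which is no bias. Its precision is poor. With a median split (48 active, 8 controls) the standard error is roughly visit SD × √2 × √(1/48 + 1/8), which is 0.54 cycles for visit SD 1 and 1.35 for visit SD 2.5. For the high-minus-low difference of two such contrasts, multiply by √2: 0.76 to 1.91 cycles. These standard errors ignore a small reduction of spread within each half.

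**The case against.** The strongest reply is that the protocol never tests high-load against low-load carriers. The endpoint is reported for all arms, both control arms are in the same table, and the mixed model in Section 8.3 compares groups, which most naturally means arms. Baseline covariates and cut-points are often left to a statistical analysis plan, and one may exist that is not shown. The trial is a pilot, and much of its reporting is descriptive anyway.

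Part of this stands. A reader who sets each active load group beside the controls in the same group is not misled. But reporting a decrease by entry load, and then its variability by entry load, invites the comparison across load groups, and nothing in the protocol ties this endpoint to a contrast with control. Taking entry load from another Day 0 assay would not remove the problem, because that assay would share the day's fluctuation.

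Three stronger readings are tempting and are not supported:
- That the low-load group must show an increase. This needs stable load and weak selection at entry. With the positive-test requirement it may stay flat or fall.
- That the trial will conclude the tea works better in heavy carriers, and that the tabulation cannot tell artefact from effect. With 16 per active arm the false gradient is often not significant, and the randomised controls in the same table allow an unbiased comparison.
- That a ceiling at Ct 40 adds to the gradient. Section 5.7 calls Ct above 40 negative but does not say how such results are coded, so any cap is an assumption.

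**Conclusion.** The point holds as a defect in how two endpoints are worded. Within any arm, the decrease by entry load is contaminated by regression to the mean, in a predictable direction: more apparent decrease at high load. The direction follows from the single Day 0 measurement. The size, about 0.5 to 2.5 cycles between halves, rests on the assumed SDs, a median split, stable load and no selection. Strong selection at entry would narrow the gap. Randomised contrasts with control within a load group are not affected, and their limit is precision. One secondary and one exploratory endpoint are concerned. The primary endpoint is not part of this point.

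**What to change.** Reword the entry-load part of both endpoints as the difference from the control arms in follow-up Ct, by entry load. Estimate it in the linear mixed model already planned, with Day 0 Ct as a continuous covariate and an arm-by-Day 0 Ct interaction, for example all active arms pooled against controls. Report the interaction with its confidence interval. State that within-arm decreases by entry load are descriptive and are not to be read as differential efficacy.

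The cost is the wording of two endpoints, a baseline covariate and an interaction term. No new data are needed. There are two drawbacks. The interaction will be imprecise with 16 controls. The model removes regression to the mean but not any ceiling effect from negative results (Ct above 40), so their handling needs to be stated alongside.

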3. METHODOLOGY

Study Design: The study is a Phase 2 randomized controlled, partial-blind, parallel group study in plasmodium infected *asymptomatic* adults 18 years and older, with 8 study arms. It will use the adapted Zelen design. The adapted Zelen design uses two steps in the consent process. In the first step, there is an informed consent from all participants for a cohort lifestyle study. After consent is obtained, baseline assessment and screening will be performed, and eligible participants randomly assigned to the different study arms. According to this consent, participants are randomized without knowledge about the detailed protocol. In the second step, only participants from the intervention group will receive the information about the intervention and the second consent will be obtained from them. The participants who will decline to participate to an intervention will continue in the cohort study, as the control group.

Duration of study: The study duration is 35 days (5 weeks) for each participant.

Treatment groups (TG):

TG 1: Group of 8 persons receiving *A. afra* infusions of 5g/1liter of water, 3drinks a day, daily for 1week (7 days) (current recommendation).

TG 2: Group of 8 persons receiving *A. afra* infusions of 5g/500ml of water, 2drinks a day, daily for 1week (7 days) (increase concentration and decrease dose frequency).

TG 3: Group of 8 persons receiving *A. afra* infusions,5g/1liter of water 3drinks a day, weekly for 4weeks (decrease dose frequency and increase length of treatment).

TG 4: Group of 8 persons receiving flavored *A. afra* infusions, 5g/1liter of water 3drinks a day, daily for1week (7 days) (current treatment with improved taste).

TG 5: Group of 8 persons flavored *A. afra* infusions, 5g/500ml of water 2drinks a day, daily for 1 week (7 days) (improved taste, increase concentration and decrease dose frequency).

- **TG 6:** Group of 8 persons receiving flavored *A. afra* infusions, 5g/1liter of water 3drinks a day, weekly for 4weeks (improved taste, decrease dose frequency and increase length of treatment);
- **TG 7**: Group of 4 persons receiving flavored placebo infusions, 5g/liter of water 3drinks a day, daily for 1week (7 days) (improved taste with no active molecule);
- **TG 8**: Group of 4 participants receiving regular tea placebo taken as desired, daily for 1 week (7 days) (Regular tea with no active molecule).

[figure not shown]

Figure 2. Screening and recruitment of study participants

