6.2 Treatment administration

After randomization and allocation, clear education, and demonstrations on how to prepare and consume the treatment will be provided to participants by the site investigator based on their randomization codes. Participants on the trial treatment arms will receive either of the Artemisia infusions of various dosage schedules and formulations, and participants on the placebo arms will drink either a flavored inactive infusion or the regular tea. The participants will take the treatment or placebo orally, under the supervision of one of the investigators (Observers). 8 observers will be assigned to follow up and assist participants on the various treatment arms (1 observer per treatment arm). The observer will encourage compliance to treatment, observe for side effects/ adverse events, and take note of participant's comments/appreciation of the treatment dosages and formulation, throughout the study period. The Observer will also effect home visits to participants when necessary (in case of loss to follow-up and difficulty to contact participant on cell phone).

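### Completion of supervised, encouraged dosing is a weak and burden-dependent proxy for acceptability, and it has no meaning in the regular-tea arm (TG8)

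*Protocol*

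**What the plan says.** Acceptability is part of the primary objective (section 2.3.1) and is the second secondary objective: "To identify the most acceptable dose concentration, dose frequency, length of treatment, and formulation (flavor) of Artemisia treatment". The outcome list in section 2.3.2 equates it with taking and finishing the treatment: "Acceptability (adherence and completion) of *Artemisia afra* treatment by dose concentration, dose frequency, length of treatment, and formulation (flavor". The matching secondary endpoint is "Proportion of people in the various treatment arms who respect and complete the prescribed treatment dosages (accepted dosage schedule and drug formulation", and an exploratory endpoint repeats it as variability between arms. No threshold for partial adherence is given.

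Section 6.2 describes intake: "The participants will take the treatment or placebo orally, under the supervision of one of the investigators (Observers". The same observer has two further tasks: "The observer will encourage compliance to treatment, observe for side effects/ adverse events, and take note of participant's comments/appreciation of the treatment dosages and formulation". Staffing is by arm: "8 observers will be assigned to follow up and assist participants on the various treatment arms (1 observer per treatment arm". No listed endpoint uses the comments and appreciation that the observer writes down.

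The treatment groups in section 3 pair each unflavoured Artemisia regimen with a flavoured one (TG1/TG4, TG2/TG5, TG3/TG6). TG8 is described as "receiving regular tea placebo taken as desired, daily for 1 week (7 days". The study description in section 3 places participants who decline an intervention in TG8. Table 4 (section 5.6) records treatment compliance and acceptability at days 7, 14, 28 and 35.

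**The concern.** The trial tries to raise the quantity by which it means to tell arms apart. "The observer will encourage compliance to treatment" is a sensible instruction when the aim is exposure to treatment. It works against an endpoint meant to show what people are willing to take, because reluctant drinking and willing drinking are scored alike.

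Three further features weaken the measure:

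- Observers are tied to arms, so a persuasive observer and a well-liked tea produce the same result, also within a flavour pair such as TG1 and TG4.
- The number of drinks to finish differs by regimen, so completion mixes burden with liking.
- TG8 has no prescribed amount, so completion there is either undefined or automatic, although the endpoint is worded for all arms. Moving decliners into TG8 also takes the clearest refusals out of the arm that was refused.

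At stake is the choice of accepted schedule and flavour, a named objective of the trial. The information cannot be recovered after the participants have finished.

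**Working it through.** **Inputs from the protocol**

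- Participants (section 8.1): 8 per active arm and 4 per control arm at each site. Total 2 × (6 × 8 + 2 × 4) = 112, which reproduces the stated figure. Over two sites this gives 16 per active arm, 32 per regimen (two arms) and 48 per flavour (three arms).
- Drinks (section 3): TG1, TG4 and TG7, 3 × 7 = 21; TG2 and TG5, 2 × 7 = 14; TG3 and TG6, 3 × 4 = 12, reading weekly as one day a week, which the label about decreased frequency supports. TG8: no number.
- Significance level 0.05 (section 8.3), taken as two-sided.

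**Assumed, not in the protocol**

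- The chance p that a given drink is taken, equal in all arms and independent between drinks, shown from 0.95 to 0.999.
- Completion means every drink.

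**Step 1: effect of the drink count alone.** Full completion = p^k for k drinks.

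| p | 21 drinks | 14 drinks | 12 drinks | Gap, 12 minus 21 (points) |
|---|---|---|---|---|
| 0.95 | 34.1% | 48.8% | 54.0% | 20 |
| 0.98 | 65.4% | 75.4% | 78.5% | 13 |
| 0.99 | 81.0% | 86.9% | 88.6% | 8 |
| 0.999 | 97.9% | 98.6% | 98.8% | 1 |

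Equal liking per drink can therefore give a regimen gap of 1 to 20 points. Within each flavour pair k is the same, so this gap is zero.

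**Step 2: ability to see a difference.** Power of the two-sided Fisher exact test at 0.05 for two completion proportions:

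| Completion | 16 v 16 | 32 v 32 | 48 v 48 |
|---|---|---|---|
| 95% v 90% | 0.8% | 2.3% | 5.8% |
| 70% v 90% | 16.8% | 41.1% | 61.3% |
| 60% v 90% | 35.9% | 74.8% | 91.3% |

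Near the ceiling that supervision and encouragement favour, the endpoint separates almost nothing. Away from it, large flavour effects can be detected when the three pairs are pooled.

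**Step 3: observer and arm.** With one observer per arm, the difference between TG1 and TG4 is the flavour effect plus the difference between two observers, and no data in the trial split the two. Section 6.2 does not say whether the eight observers cover both sites or each site has eight; in both cases observers are nested in arms. Pooling three pairs averages this effect but does not remove it.

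**Step 4: TG8.** The endpoint needs a prescribed dosage as its reference. Section 3 lets TG8 drink as desired, so no reference exists.

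**The case against.** A reader might infer that the endpoint cannot show which regimen or flavour people accept. The protocol does not support that.

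- **Flavour.** Paired arms have equal drink counts, and the pooled comparison has 61% power for 70% against 90%. Nothing in the protocol says that completion will be near 100%.
- **Regimen.** The second secondary objective asks about frequency and length. That 21 drinks are harder to finish than 12 is partly the answer sought. Calling two such regimens equally accepted presumes that acceptance means liking per drink, which is not the protocol's definition.
- **Size.** The 13 to 20 point gap needs p of 0.95 to 0.98, and the ceiling needs p close to 1. They cannot both apply in full. If non-completion clusters in people who stop altogether, p^k overstates the gap.
- **Supervision.** Section 6.2 also teaches participants to prepare the tea and foresees telephone contact and home visits when needed, so an observer may not be present at every drink.
- **Threshold.** None is stated. A cut-off may sit in a statistical analysis plan that is not at hand.
- **Other information.** Withdrawals for reasons other than severe adverse events are a secondary endpoint by arm, and appreciation is noted.

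All of this stands against the strong reading. It does not answer the narrower point: the only endpoint that carries acceptability counts encouraged drinking as acceptance, is tied to the observer, mixes burden with liking, and includes an arm where it has no meaning.

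Two further inferences should also be left aside. Scoring each drink before any encouragement is given would need an observer at every drink and would change the procedure in section 6.2. What it means to receive all doses in TG8 for the Per Protocol set (section 8.2.3) is a small matter that the planned blind review of violations can settle.

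**Conclusion.** The point holds in a limited form. Completion under supervised and encouraged intake is a weak proxy for acceptability. It is confounded with the observer in every contrast between arms, and in regimen contrasts it includes burden. The count-driven regimen gap runs from 1 point (p = 0.999) to 20 points (p = 0.95), assuming equal and independent chances per drink and the one-day-a-week reading of the weekly arms; it is zero for flavour. The loss of discrimination depends on how close supervision brings completion to 100%, which the protocol does not state. That the endpoint is undefined in TG8 follows from the text alone. This is a correctable weakness in how a named objective is measured; it does not show that the objective is out of reach.

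**What to change.** 1. Add one fixed rating of taste and willingness to repeat as an acceptability endpoint, completed by the participant at the end of the course. It replaces the free notes on comments and appreciation as the source for acceptability.
2. Report the percentage of prescribed drinks taken alongside full completion, from the compliance records already planned in Table 4. State that regimen differences in completion include burden.
3. Limit the adherence and acceptability endpoint to arms with a prescribed dosage (TG1 to TG7), by randomised arm. Count those who decline after allocation as not accepting in their assigned arm. The denominator must then be all those randomised to these arms, because the Full Analysis Population in section 8.2.3 requires a dose received.

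The cost is one extra worksheet item and revised endpoint wording; dosing and supervision stay as they are. If an observer collects the rating, it too is confounded with the arm, so self-completion matters. Completion itself keeps that confounding as long as observers are assigned by arm.
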